9.3.4. Analysis of the Primary Efficacy Endpoint

Primary Endpoint is determined by meeting the success criterion for SYS and DIA BP as defined by ISO 81060-2: 2013

9.5. Sample Size

As determined in ISO 81060-2 / 2013; a reference invasive BP monitoring equipment clinical investigation shall consist of a minimum of 15 patients. For each patient shall be a minimum of 150 valid BP measurements in the clinical investigation.

The goal sample size is 15 patients. It is expected that 25 patients will need to be screened to obtain the desired sample size.

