| Population | Patients admitted to the Intensive Care Unit who are already fitted with an invasive Arterial Line (A Line) are eligible for the trial, and no volunteer candidates for an A Line are requested. Sample size is expected to be approximately 15 patients. |
| Study Sites | NYU Langone Health Surgical Intensive Care Unit, Cardiovascular Intensive Care Unit, Neurologic Intensive Care Unit and NYU Langone Brooklyn Surgical Intensive Care Unit and Neurologic Intensive Care Unit |
| Number of participants | Total sample size is expected to be 15 patients. |
| Description of Study Agent/Procedure | The device is a band intended to be worn on the wrist for intermittent blood pressure measurements. The device applies no inflatable mechanics or moving parts. The wristband is watertight and can be worn as any type of bracelet. |
| Reference Therapy | The investigational wristband is being compared to an intra-arterial blood pressure monitor. |
| Key Procedures | Wristband application for 30 minutes. |
| Statistical Analysis | For each of the subjects, 10 intra-arterial blood pressure measurements will be collected and 10 wristband measurements will be collected at the same time points. |

| | |
|--|--|
| | 
Systolic and diastolic blood pressure measurements will be compared using an acceptable standard deviation of 10 mm Hg (+/-5 mm Hg). Mean arterial pressure measurements will be compared using an acceptable standard deviation of 5 mm Hg (+/- 2.5 mm Hg).
 
The percentage of blood pressure measurements falling within the acceptable standard deviation will be compared. The percentage of blood pressure measurements for each patient falling within the acceptable standard deviation will also be compared.
 |
|--|--|

Schematic of Study Design

1. Patients in the ICU with an intra-arterial blood pressure monitor already in place will be considered as subjects.
2. Verbal consent to participate will be obtained.
3. The blood pressure wristband will be applied to one wrist to allow for blood pressure measurements to be obtained and recorded. The blood pressure wristband will then be applied to the contralateral wrist for measurements. The total time of device application is expected to be approximately 30 minutes.
4. Demographics of the subject will be anonymous collected – height, weight, age, current medications, and general condition.
5. Blood pressure measurements from both the wristband and the intra-arterial blood pressure monitor will be compared.

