4.1. Description of Study Design

1. A medical professional will measure simultaneous non-invasive auscultatory readings to determine the lateral difference for later adjustment of calculation accordingly. Calculation of lateral difference is provided in section (**Error! Reference source not found.**). All data from a subject shall be excluded if: i) the lateral difference of the reference systolic BP readings is more than 15 mmHg (2,00 kPa); or ii) the lateral difference of the reference diastolic BP readings is more than 10 mmHg (1,33 kPa).
2. If subject's reading is eligible, the medical professional or research personnel will place the LiveMetric wristband on the opposite limb than the one having the A-line, providing the location of the placement has intact skin.
3. During the measurement stage, BP values are simultaneously recorded from the reference invasive A-line and the LiveMetric device. In addition, other vital signs from the monitoring equipment can be collected as available (ECG, Respiratory rate, Pleth, and HR). The invasive BP values and other vital signs are captured from the Vital Signs Monitor (available in the patient's room) and the LiveMetric device. A measurement session of 30 minutes will be conducted for each subject. During the measurements, no information from the device will be provided to the investigator or study personnel. All the data will be processed and analyzed post-measurement according to the following considerations as required by the standard: only up to 10 consecutive measurements per subject will be analyzed; measurement will be made over 30 seconds of recording; consecutive meas-

urement will be considered as the next 30 seconds following at least a 60 second interval. Measurement (data points) is defined as recording or acquisition of signal from the monitor. The medical professional will take off the wristband at the end of this process.

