4. All measurements will be processed and analyzed retrospectively according to the requirements of the standard (ISO 81060-2) as detailed below in section (**Error! Reference source not found.**). A 30-minute session of measurements will be conducted for each subject. All the data will be processed and analyzed post measurement according to the following considerations as required by the standard; only up to 10 consecutive measurements per subject will be analyzed; measurement will be made over 30 seconds of recording; consecutive measurement will be considered as the next 30 seconds following at least a 60 second interval.
5. All data points recoded during the first phase will be sent for processing and calibrating the algorithm. All the data points recorded during the second stage will be post processed by algorithm and results will be analyzed by an unbiased third party (bio-statistician).
6. Demographics of the subject will be anonymous collected from the electronic medical record – height, weight, age, current medications, and general condition.
7. Blood pressure measurements from both the wristband and the intra-arterial blood pressure monitor will be compared.

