4.2. Study Endpoints

4.2.1. Primary Study Endpoints

The study endpoint will be the time when 10 blood pressure measurements have been obtained from a subject wearing the wristband.

5. Study Enrollment and Withdrawal

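### Section 9.5 sets a minimum of 150 valid readings for each patient, but the design analyses at most 10 per patient and a 30-minute session holds at most 20

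*Combined protocol and SAP*

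**What the plan says.** Section 9.5 attributes two minimums to ISO 81060-2:2013. The first is 15 patients, which is also the recruitment goal. The second reads: "For each patient shall be a minimum of 150 valid BP measurements in the clinical investigation".

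The rest of the protocol works with 10 per patient:

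- Section 4.1, items 3 and 4: "only up to 10 consecutive measurements per subject will be analyzed".
- Protocol Summary and section 9.1: "10 intra-arterial blood pressure measurements will be collected and 10 wristband measurements will be collected" for each subject.
- Section 4.2.1 sets the endpoint as "the time when 10 blood pressure measurements have been obtained from a subject wearing the wristband".

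Section 4.1 also fixes the timing. "A measurement session of 30 minutes will be conducted for each subject", each measurement spans 30 seconds of recording, and "consecutive measurement will be considered as the next 30 seconds following at least a 60 second interval".

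The opening of section 9 makes a data point conditional on the spread of the A-line readings: below 20 mmHg for systolic and below 12 mmHg for diastolic pressure. No section says what happens to the count when a window fails these limits.

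**The concern.** Section 9.5 is the plan's only justification of its sample size. It is presented as a requirement of the standard that also defines the primary success criterion (9.3.4). A per-patient minimum 15 times the per-patient maximum cannot be complied with, so anyone checking conduct against 9.5 as written would find every patient deficient.

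Correcting the unit exposes a smaller gap. If 150 is a total, 15 patients capped at 10 reach it only when every patient supplies 10 valid windows. Whether a failed window may be replaced then decides whether the minimum is met, and the plan does not say.

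**Working it through.** **Inputs.** Session 30 min = 1,800 s; recording 30 s; gap at least 60 s; cap 10 per subject (all 4.1). Patients 15; minimum 150 (9.5). Enrolment about 20 (5.6).

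**1. Reproducing the figure of 150.** Patients × measurements per patient = 15 × 10 = 150. The figure reproduces exactly as a study total. Read per patient, the study would need 15 × 150 = 2,250.

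**2. Session capacity.** Find the largest k with 30k + 60(k − 1) ≤ 1,800. This is floor((1,800 − 30)/90) + 1 = 20.

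| Windows | Time needed |
|---|---|
| 10 | 10 × 30 + 9 × 60 = 840 s = 14 min |
| 20 | 20 × 30 + 19 × 60 = 1,740 s = 29 min |
| 150 | 150 × 30 + 149 × 60 = 13,440 s = 224 min |

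**3. Looser readings.** If the 60 s runs from start to start, the session holds floor((1,800 − 30)/60) + 1 = 30 windows. With no gap it holds 1,800/30 = 60. Neither reaches 150. Section 9.3.1 records beat to beat, and single beats could exceed 150 in half an hour, but 4.1 makes a measurement a 30-second recording and the cap of 10 still applies.

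**4. A tighter reading.** Item 3 of the Schematic of Study Design puts the band on one wrist and then on the other within about 30 minutes in total. Section 4.1 uses only the limb opposite the A-line. If the time were split equally (an assumption; no split is given), one wrist would have 900 s and hold floor((900 − 30)/90) + 1 = 10 windows, with none spare.

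**5. Margin when 150 is a total.** With 15 patients and no replacement, each failed window lowers the total by one, so a single failure gives 149. The documents give no failure rate. Purely as illustration, assumed rates of 5%, 10% and 20% leave on average 150 × 0.95 = 142.5, 150 × 0.90 = 135 and 150 × 0.80 = 120 valid windows. With one-wrist use under 4.1 there are up to 20 − 10 = 10 spare windows per patient; under the equal split in step 4 there are none.

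**The case against.** The strongest reply is that this is a slip in one phrase. The summary, 4.1, 4.2.1 and 9.1 agree on 10, nobody following 4.1 would try to collect 150 per patient, and the formulas in 9.3.3 run at any n. This stands as to consequence: 224 minutes and 2,250 readings describe a requirement that was probably never intended. It does not remove the error, because 9.5 is where compliance with the minimum is defined.

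A reader might infer that the analyst may choose any 10 of 20 windows. The documents do not support that. Section 4.1 speaks of consecutive measurements, and 4.2.1 ends at 10 obtained, which points to the first 10. During measurement "no information from the device will be provided to the investigator or study personnel", for second-stage data "results will be analyzed by an unbiased third party (bio-statistician", and window validity rests on the A-line range. What stays open is only whether a failed window counts towards the 10.

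It may also be said that a margin exists, since 15 is a minimum and 5.6 enrols about 20. That margin is set against patients who are not evaluable, and sections 5.7.2 and 13.2 replace whole subjects rather than windows. Still, evaluable is not defined and could be taken to include having 10 valid windows, so the point is partly answered.

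**Conclusion.** The minimum in 9.5 is wrong as written. It is 15 times the analysis cap and at least 7.5 times (150/20) what a session can hold under the stated timing. This part rests on the protocol's own figures alone.

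That 150 is a study total is an inference from 15 × 10 = 150; the standard was not available to check it. The missing rule for failed windows matters only if that inference is right, and how much it matters depends on a failure rate that is not given and on which wrist description applies.

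A reader might go further and conclude that the study is likely to miss 150, or is too small. That does not follow. Any probability of reaching 150 would need an assumed failure rate and an assumed clustering of failures within patients, on top of the inferred total. Such figures are illustrative and carry no weight in this conclusion. No bias is claimed. The point should be fixed because a stated sample-size requirement cannot be met and the repair is cheap.

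**What to change.** 1. **9.5:** after checking the cited standard, restate the minimum as at least 15 evaluable patients and at least 150 valid determinations in total, with at most 10 per patient.
2. **4.1 and 4.2.1:** add one line: a window that fails the A-line limits in section 9 is passed over, the first 10 valid windows in time order are used, and validity is judged from A-line data alone.
3. **5.6:** keep enrolment at about 20. Do not add a rule that recruitment runs until 150 is reached, because that would conflict with 5.6 as it stands. If 150 is not reached, report the number attained.
4. **4.1 and the Schematic:** reconcile the one-wrist and two-wrist descriptions, since they decide how many spare windows exist.
5. **5.4 and 9.5:** state one screening figure (now 20 and 25). This is minor.

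The cost is one amendment of wording, with the IRB approval that 12.2 requires. Target sample size, enrolment and session length do not change.

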9.6. Measures to Minimize Bias

Blinding is not an option in this investigation. All subjects will utilize both the intra-arterial blood pressure monitor which is already in place and the wristband that is applied during the study.

10. Source Documents and Access to Source Data/Documents

Source data is all information, original records of clinical findings, observations, or other activities in a clinical trial necessary for the reconstruction and evaluation of the trial. Source data are contained in source documents. Examples of these original documents, and data records include: hospital records, clinical and office charts, laboratory notes, memoranda, subjects' diaries or evaluation checklists, pharmacy dispensing records, recorded data from automated instruments, copies or transcriptions certified after verification as being accurate and complete, microfiches, photographic negatives, microfilm or magnetic media, x-rays, subject files, and records kept at the pharmacy, at the laboratories, and at medico-technical departments involved in the clinical trial. It is acceptable to use CRFs as source documents. If this is the case, it should be stated in this section what data will be collected on CRFs and what data will be collected from other sources.

The study case report form (CRF) is the primary data collection instrument for the study. All data requested on the CRF must be recorded. All missing data must be explained. If a space on the CRF is left blank because the procedure was not done or the question was not asked, write "N/D". If the item is not applicable to the individual case, write "N/A". All entries should be printed legibly in black ink. If any entry error has been made, to correct such an error, draw a single straight line through the incorrect entry and enter the correct data above it. All such changes must be initialed and dated. **DO NOT ERASE OR WHITE OUT ERRORS.** For clarification of illegible or uncertain entries, print the clarification above the item, then initial and date it.

Access to study records will be limited to IRB-approved members of the study team. The investigator will permit study-related monitoring, audits, and inspections by the IRB/EC, the sponsor, government regulatory bodies, and University compliance and quality assurance groups of all study related documents (e.g. source documents, regulatory documents, data collection instruments, study data etc.). The investigator will ensure the capability for inspections of applicable study-related facilities (e.g. pharmacy, diagnostic laboratory, etc.).

Participation as an investigator in this study implies acceptance of potential inspection by government regulatory authorities and applicable University compliance and quality assurance offices.

11. Quality Assurance and Quality Control

QC procedures will be implemented beginning with the data entry system and data QC checks that will be run on the database will be generated. Any missing data or data anomalies will be communicated to the site(s) for clarification/resolution.

Following written SOPs, the monitors will verify that the clinical trial is conducted and data are generated, documented (recorded), and reported in compliance with the protocol, GCP, and the applicable regulatory requirements (e.g., Good Laboratory Practices (GLP), Good Manufacturing Practices (GMP)).

The investigational site will provide direct access to all trial related sites, source data/documents, and reports for the purpose of monitoring and auditing by the sponsor, and inspection by local and regulatory authorities.

12. Ethics/Protection of Human Subjects

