7.7. Safety Oversight

It is the responsibility of the Principal Investigator to oversee the safety of the study at his/her site. This safety monitoring will include careful assessment and appropriate reporting of adverse events as noted above, as well as the construction and implementation of a site data and safety-monitoring plan. Medical monitoring will include a regular assessment of the number and type of serious adverse events.

8. Clinical Monitoring

PI will be conducting monitoring to ensure safety of subjects.

9. Statistical Considerations

Data from the A-line monitor and from the LiveMetric device shall be collected and processed using a validated Software. Categorical parameters shall be presented in percentages and will be compared using X² testing. Continuous variables shall be reported as mean \pm standard deviation and will be compared using the Student's t-test. Correlation shall be determined via linear regression analysis. Agreement shall be determined via the Bland and Altman technique. The analysis shall be conducted for intermittent values by applying the reference ISO 81060-2:2013.

The LiveMetric device shall provide values for each intermittent session and shall be compared to a range measured by the A-Line (data point). The data point is defined as the interval between the lower and higher value read by the A-Line, providing: the interval is no less than 30 seconds; the difference range from the reference device is less than the permissible highest range of 20 mmHg for SYS and 12 mmHg for DIA. Should the LiveMetric device read within the same range as the A-line, then the reading is considered accurate. However, if the reading is not within the defined range, then the error rate is defined as the range in mmHg between the closest edges of the reference reading to the values obtained by the LiveMetric device

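### Section 9.6 rules out blinding, but second-stage wristband values are computed after the session and could be produced masked to the A-line; the plan does not say that they will be

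*Combined protocol and SAP*

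**What the plan says.** **Blinding.** Section 9.6 states "Blinding is not an option in this investigation". Its only reason is that each subject has both the arterial line and the wristband.

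**Capture.** Under 4.1, step 3, "BP values are simultaneously recorded from the reference invasive A-line and the LiveMetric device". The same step masks the bedside: "During the measurements, no information from the device will be provided to the investigator or study personnel".

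**Processing.** Section 4.1, step 5, treats two stages differently. For the first, "All data points recoded during the first phase will be sent for processing and calibrating the algorithm". For the second, "All the data points recorded during the second stage will be post processed by algorithm and results will be analyzed by an unbiased third party". The plan does not say who runs the algorithm in the second stage, or which data that party holds.

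**The term data point.** It has three uses:
- 4.1, step 3: "Measurement (data points) is defined as recording or acquisition of signal from the monitor".
- The opening text of section 9: "The data point is defined as the interval between the lower and higher value read by the A-Line".
- 9.3.1: the wristband's own recording over the same 30 seconds.

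**After a failed test.** Section 9.3.3 calls for the algorithm to be modified and then tested again on fresh data.

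**The concern.** In an accuracy study the index result should be produced without knowledge of the reference result. Here the index result is not a reading taken at the bedside. It is computed later from stored data, and that computation is the step that most needs masking. Section 9.6 considers only whether patients can be kept from having both devices, and concludes that nothing can be masked.

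If whoever runs the algorithm can also see the A-line, several choices could be made against the known answer: rejecting poor signal, re-running a recording, applying an offset, or choosing which readings to keep. Each tends to improve apparent agreement. The plan's conclusions on accuracy (the ISO criterion in 9.3.4 and the target in 9.2 of more than 90% of readings within limits) would then partly reflect access to the reference.

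**Working it through.** No sample size, power or error rate in the plan depends on this point, so there is no stated figure to reproduce. The check is mainly a reading of the data flow, followed by an illustration of size.

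**1. Where the test value is made.** Steps 3 to 5 of 4.1 place processing after the session. Section 6.1.2 agrees, since it describes the download as signals. Two places read differently: 6.2 speaks of wristband pressure measurements being downloaded, and 9.3.1 of a beat-to-beat reading recorded from the device. Even so, step 5 passes second-stage data through the algorithm afterwards. Masking at that point is feasible.

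**2. What each safeguard covers.**

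| Safeguard | What it masks or limits | Does it mask the algorithm step? |
|---|---|---|
| Device output hidden during the session (4.1, step 3) | Bedside staff from the wristband | No. It also shows that some masking is possible, contrary to 9.6 |
| Third-party biostatistician (4.1, step 5) | Analysis of results that already exist | No |
| New data after a failed test (9.3.3) | Re-tuning on a failed data set | No. It protects the retest, not the first run |

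**3. Whether the reference is withheld.** No section says that A-line values are removed or held back before second-stage processing, or that wristband values are fixed before the two are linked. The opening of section 9 has data from both devices collected and processed with validated software, with no separation stated. The three uses of data point do not settle what enters the algorithm.

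**4. Size, illustration A (assumed inputs).** Let the error SD be 8 mmHg and let a share p of its variance lie between patients. Neither figure is in the documents. Removing each patient's offset leaves SD = √[64 × (1 − p)]:
- p = 0.25: √48 = 6.9 mmHg
- p = 0.50: √32 = 5.7 mmHg
- p = 0.75: √16 = 4.0 mmHg

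These are SDs of raw differences. Section 9.3.1 scores an error as zero inside the A-line mean ± 1 SD, and otherwise as the distance to the nearer limit. The SD that the plan would report is therefore not obtained by subtracting variances.

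**5. Size, illustration B (assumed inputs).** Sections 9.1 and 9.2 together aim for more than 90% of SYS and DIA readings within ±5 mmHg. With normal errors and no bias this needs an SD of 5 / 1.645 = 3.04 mmHg. Let b and w be the between- and within-patient error SDs, with ten readings per patient:
- masked share within ±5 = 2Φ(5 / √(b² + w²)) − 1
- share after fitting each patient's offset to the A-line = 2Φ(5 / (w√0.9)) − 1

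| b, w (mmHg) | Masked | Offset fitted |
|---|---|---|
| 2, 3 | 83% | 92% |
| 4, 3 | 68% | 92% |
| 6, 3 | 54% | 92% |
| 4, 4 | 62% | 81% |
| 6, 4 | 51% | 81% |
| 6, 2 | 57% | 99% |

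For some inputs, access to the reference would decide whether the 90% target is met. For others (w = 4) it would not. This too uses raw differences, not the 9.3.1 rule.

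**The case against.** The strongest reply is that the point rests on silence. Four stronger readings are tempting, and the documents do not support them.

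- **That the plan hands the A-line to the processor.** A reader might infer this by putting the section 9 definition of data point into step 5. But the sending in step 5 concerns first-phase data, where calibration needs the reference. For the second stage only processing is stated, with no recipient. Section 9.3.1 also uses the term for the wristband, and an algorithm that processes A-line intervals would make little sense. The text shows inconsistent terms and an omission, not an instruction.
- **That agreement will be overstated.** The plan leaves access open; it does not say that access is used. No section provides for a per-patient offset fitted to the A-line in the second stage. If the algorithm version and the windows were fixed, mainly signal rejection and re-runs would remain. The supportable word is could.
- **That an SD of 5.7 mmHg is an upper bound on the effect.** It is one value from assumed inputs. Selective rejection could reduce within-patient error as well, and the 9.3.1 rule changes the scale.
- **That bedside masking is irrelevant because the A-line is recorded automatically.** Section 13.1 (Data Collection and Management Responsibilities) says that it is. Section 6.2 has values recorded from the monitor screen, which may mean transcription. If so, hiding device output is a useful safeguard. Section 6.2 also describes separate capture routes for the two devices, but separate capture is not masking.

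What remains after these corrections is that 9.6 gives a reason that does not apply to the step that matters, and no other section masks that step.

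**Conclusion.** The point holds in a limited form. Section 9.6 treats blinding as impossible, although second-stage wristband values are produced after the session and that step can be masked. The plan does not state that it will be, and its existing safeguards act elsewhere. Any bias would probably favour agreement. Its size cannot be calculated from the documents: no error SD, variance split or processing rule is given. The range of 6.9 to 4.0 mmHg from an assumed 8 mmHg, and the percentages within ±5 mmHg, show only that the effect could matter.

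This is a change that should be made, not a fatal flaw. It concerns an omission in a pilot study, and the remedy is cheap.

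**What to change.** 1. **Rewrite 9.6** to say that patients and bedside staff cannot be kept unaware of the devices, but that second-stage wristband values are produced masked to the A-line.
2. **Amend 4.1, step 5.** Only time-stamped wristband signals go to the party running the algorithm on second-stage data. The A-line recording goes directly to the independent biostatistician.
3. **Fix values before linkage.** The processor returns one SYS and one DIA value, or an entry of *no reading*, for each window. The biostatistician merges the files only after these are received and fixed, and then applies the lateral-difference adjustment (9.3.3) and the reference-range limits (section 9).
4. **Reconcile the supporting text.** Use data point in one sense throughout. Settle whether the A-line is captured from the screen (6.2) or automatically (13.1, Data Collection and Management Responsibilities). Align 9.2.1, which gives all analysis to one named physician, with the third-party biostatistician in step 5.

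The cost is protocol wording and one file-handling step. The biostatistician is already planned, so no extra staff are needed, and nothing changes for patients.
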